3.9 Summary of Background and Data on Linezolid

S. aureus bacteraemia remains a life-threatening condition with high morbidity and a mortality of up to 30% despite antibiotic therapy. Emerging evidence suggests that bacterial virulence factors significantly contribute to organ damage and poor patient outcomes. Linezolid, a well-established antibiotic with anti-virulence factor properties, offers a promising adjunctive treatment option. Preclinical studies demonstrate that linezolid effectively inhibits *S. aureus* virulence factor expression and improves survival in animal models. Clinical data support its safety and efficacy in various *S. aureus* infections, including pneumonia and bacteraemia.

Since its approval more than 20 years ago, the risk profile of linezolid has been well-documented. The approved treatment duration varies from 10-28 days depending on the cause and location of the infection. Notable adverse events of linezolid are myelosuppression, serotonin syndrome, kidney injury, *C. difficile*-associated diarrhoea, lactic acidosis, and neuropathy. Myelosuppression is typically associated with prolonged use (≥ 10 days) and is reversible upon linezolid discontinuation. Serotonin syndrome is very rare with monotherapy and remains uncommon even with concurrent serotonergic medications. Renal adverse effects including increased creatinine and rare cases of renal failure have been reported with linezolid use. Like many antibiotics, linezolid has been associated with *C. difficile*-associated diarrhoea, which can range from mild diarrhoea to fatal colitis. Lactic acidosis is rare but serious and is linked to extended treatment durations. Neuropathy has been described in patients with treatment durations exceeding the maximum recommendation of 28 days and is thus very unlikely to occur in this trial.

Since linezolid will be administered for only 5 days in the LIPS trial, a favourable safety profile is expected. In addition, hospitalization of study participants facilitates a close monitoring for any adverse events.

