7. STUDY POPULATION

7.1 Eligibility criteria

Inclusion criteria:

- *S. aureus* grown from at least one blood culture
- Hospitalised at a participating centre
- ≥ 18 years old
- Written informed consent or fulfilling criteria for an emergency exception from informed consent requirements

Exclusion criteria:

- Administration of the initial drug treatment not feasible within 72 hours since the collection of the first positive blood culture with *S. aureus*
- Documented history of positive blood cultures for *S. aureus* occurring between 72 hours and 180 days prior to the eligibility assessment
- Necrotising fasciitis
- Currently receiving linezolid or clindamycin
- Use of any monoamine oxidase A or B inhibitor within the last two weeks
- Known hypersensitivity to linezolid or any other ingredients of the study drugs
- Current severe thrombocytopenia (i.e. $<30 \times 10^9/l$)
- Oral application of study drug not possible (per mouth or per gastric tube)
- Currently breastfeeding
- Local treating team believes that death is imminent and inevitable
- Patient is receiving end of life care and antibiotic treatment is not considered appropriate
- Local treating team believes that participation in the study is not in the best interest of the patient
- Any indication that the patient is unwilling to participate in the study including an advance directive stating such unwillingness

General:

Patients taking serotonergic drugs such as selective serotonin reuptake inhibitors (SSRI) or tricyclic antidepressants are not generally excluded. See detailed information on risk assessment and precautions in chapter 8.6 *Trial specific preventive measures*.

Pregnant women will not be excluded from study participation per se, as linezolid is not formally contraindicated during pregnancy. Limited data exist on the treatment of pregnant women with linezolid, mainly from clinical trials in treating multidrug-resistant tuberculosis. In 31 pregnancies under linezolid exposure, none reported foetal toxicity.⁹⁵ In the event of pregnancy, the treating physician and the patient (or the patient's next of kin) will assess whether the potential benefits outweigh the potential risks to the foetus.

Linezolid has been shown to pass into breast milk and accordingly, breastfeeding should be discontinued prior to and throughout administration of linezolid.

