³ Choose the result that represents the highest level recorded between day 6-14.

⁴ Linezolid trough concentration is only measured in a subset of participants in participating centres.

⁵ Adverse events of special interest until day 7 include: serotonin toxicity, myelosuppression, hyperlactataemia; until day 14: acute kidney injury; until day 90: C. difficile-associated diarrhoea.

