Acute kidney injury according to the modified Kidney Disease Improving Global Outcomes (KDIGO) stage 1 is defined as an increase in serum creatinine of $\geq 26.5 \mu\text{mol/L}$ from randomisation (baseline) to study day 5 or an increase in serum creatinine by 1.5 times or more the level of randomisation within 14 days of

randomisation. To collect this outcome, the serum creatinine at baseline (on randomisation day 1 or the calendar day prior to randomisation), day 5 (± 1 day), and only if participant remains hospitalised, at day 14 (± 3 days) will be documented in the eCRF. The values will be captured from available data in the hospital information system or from the participant's primary care physician, respectively.

- *C. difficile*-associated diarrhoea within 90 days.

The treating clinicians will assess for *C. difficile* infection based on the centre-specific diagnostic algorithm if clinical suspicion arises due to diarrhoea during antibiotic treatment. *C. difficile* infection will be evaluated on day 14, at discharge, and on day 90 by reviewing the participant's electronic health records. If a participant reports severe diarrhoea during a 90-day follow-up phone call, occurring after discharge and managed outside the centre, the responsible physician may be contacted to determine if a *C. difficile* infection was diagnosed.

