11.4.5 Safety analysis

The following adverse events and safety outcomes will be analysed descriptively by study group:

- Serious adverse reactions or serious adverse events in the 90 days following study entry
- The following adverse events of special interest until 14 days after study entry during the index hospital stay:
 - Clinical signs compatible with serotonin syndrome
 - Laboratory signs of haematotoxicity
- Acute kidney injury defined using modified Kidney Disease Improving Global Outcomes (KDIGO) criteria, modified according to SNAP trial:
 - Increase in serum creatinine by 26.5 µmol/l or more at any time from baseline entry to day 5

OR

- Increase in serum creatinine by 1.5 times or more the level at study entry (baseline) within 14 days of study entry
- *Clostridioides difficile*-associated diarrhoea

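### AKI is defined by creatinine rise alone with no rule for renal replacement, so draw timing in participants on maintenance dialysis can produce false AKI events and some early new dialysis starts can be missed

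*Protocol*

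**What the plan says.** Protocol 9.2.4.1 gives the definition: "Acute kidney injury according to the modified Kidney Disease Improving Global Outcomes (KDIGO) stage 1 is defined as an increase in serum creatinine of" at least 26.5 µmol/L from randomisation to day 5, or "increase in serum creatinine by 1.5 times or more the level of randomisation within 14 days of" randomisation. Section 11.4.5 repeats both limbs. It words the first as a rise of 26.5 µmol/L "or more at any time from baseline entry to day 5" and the second as "Increase in serum creatinine by 1.5 times or more the level at study entry (baseline) within 14 days of study entry", and says the criteria follow the SNAP trial's modification. Neither section has a renal-replacement limb or a rule for participants already on dialysis.

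The data named for the outcome are creatinine values only. Section 9.2.4.1 begins "To collect this outcome, the serum creatinine at baseline" and adds day 5 (±1) and, if the participant is still in hospital, day 14 (±3). A footnote to the schedule in 9.1 says of the late value: "Choose the result that represents the highest level recorded between day 6-14".

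The exclusion list in 7.1 (and in the synopsis) contains one laboratory criterion, "Current severe thrombocytopenia". It has no creatinine, eGFR or dialysis criterion, and the protocol text supplied does not mention dialysis. Section 3.9 gives the reason for tracking the kidney: "Renal adverse effects including increased creatinine and rare cases of renal failure have been reported with linezolid use".

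**The concern.** A creatinine-only rule assumes that the participant's own kidneys set the creatinine level. Under maintenance dialysis the dialysis schedule largely sets it. A baseline drawn soon after a session and a day-5 value drawn before the next one will show a rise that says nothing about injury, and the printed rule counts it as AKI. Such events should arise in both arms at a rate unrelated to allocation. They inflate both percentages and pull the ratio towards 1.

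The opposite error is possible when dialysis is new. Treatment lowers creatinine, so if the only recorded early value comes after the start, a participant with severe renal failure may satisfy neither limb.

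AKI is a pre-specified event of special interest for a drug whose renal effects the protocol itself lists. Safety outcomes are also summarised for the DSMB after 50 and 200 participants (11.4.4), when a few spurious events weigh more.

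**Working it through.** The protocol states no AKI rate and no dialysis share, so there is no figure of its own to reproduce. The inputs from the document are the two limbs (9.2.4.1, 11.4.5), the collected values (9.1, 9.2.4.1) and 606 participants, 303 per arm (11.2). All creatinine courses, dialysis shares and AKI risks below are assumptions.

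**1. How easily the absolute limb is met.** Required relative rise = 26.5 / baseline. At 300 µmol/L: 26.5/300 = 8.8%. At 700 µmol/L: 26.5/700 = 3.8%. Above 26.5/0.5 = 53 µmol/L the absolute limb is the easier one up to day 5.

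**2. The printed rule applied to assumed courses (µmol/L).**

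| Course | Baseline | Day 5 | Day 6-14 maximum | Rise ≥26.5 | Ratio ≥1.5 | Scored |
|---|---|---|---|---|---|---|
| Maintenance dialysis, after then before a session | 350 | 600 | – | yes | yes | AKI |
| Same, smaller swing | 500 | 530 | – | yes | no | AKI |
| Same, draws reversed | 600 | 350 | – | no | no | no AKI |
| New dialysis about day 3 | 300 | 220 | 250 | no | no | no AKI |
| New dialysis about day 3 | 200 | 215 | 240 | no | no | no AKI |

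In the first three rows the draw times decide the result. The last two rows hold only if no higher value before dialysis was recorded.

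**3. How often timing alone flags a participant.** Assume sessions at midday on Monday, Wednesday and Friday, draws at 07:00, the same level after every session, and a rise of 80-180 µmol/L per day between sessions. Time since the last session is then 19 h (Tue, Thu, Sat), 43 h (Wed, Fri, Sun) or 67 h (Mon). Pair each possible day-1 weekday with day 4, 5 and 6, which gives 7 × 3 = 21 pairs. Those that gain at least one dialysis-free day (at least 80 µmol/L, above 26.5) are Tue→Fri, Tue→Sun, Wed→Mon, Thu→Sun, Thu→Mon, Fri→Mon and Sat→Wed. That is 7/21 = 33%.

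If instead each session removes an assumed 50-70% and the weekly cycle is run to steady state, 7 to 11 of 21 pairs (33-52%) meet the absolute limb. Only 1 to 3 of 21 reach 1.5-fold. One third is therefore the low end for the first limb, and the second limb is met only sometimes by day 5 (±1). The highest day 6-14 value adds some chance of meeting it. With an assumed post-session level of 250 µmol/L, a 19-h baseline against a 67-h peak gives (250 + 80×67/24)/(250 + 80×19/24) = 1.51, or 1.92 at 180 µmol/L per day.

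**4. Number of false events.** At 5% on maintenance dialysis, 606 × 0.05 = 30.3, and 30.3 × 7/21 = 10.1. At 10%, 60.6 × 7/21 = 20.2. With 11/21 instead, the figures are 15.9 and 31.7.

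**5. Dilution.** Let d be the dialysis share and f the flagged share, with assumed true AKI risks of 10% and 15% in everyone else (ratio 1.50). The observed risk is (1−d)×risk + d×f.
- d = 5%, f = 25%: 0.1075 and 0.155, ratio 1.44.
- d = 10%, f = 50%: 0.140 and 0.185, ratio 1.32.
- Over d = 2-15% and f = 25-50% the ratio runs from 1.48 to 1.27.

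**6. Which new dialysis starts are missed.** A start on days 6-14 is normally preceded by a peak, and the schedule footnote keeps the highest value of that window. A start before the day-5 (±1) draw is different. Section 11.4.5 would count a rise at any time up to day 5, but 9.2.4.1 documents only baseline and day 5 (±1), so the peak may not be in the data.

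**The case against.** The strongest reply is that this is one descriptive row. AKI is not tested and is not itself a DOOR component; it reaches the primary outcome only as a serious adverse reaction or through study drug discontinuation (5.1). The noise is unrelated to blinded allocation, so it favours neither arm. The definition is deliberately aligned with SNAP, whose text is not available here, and denominators of safety tables are often left to the SAP. All of this limits the consequence. It does not remove the error, because the protocol fixes the operative rule twice, and that rule gives wrong results in participants it admits.

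Three stronger readings are tempting, and the documents do not support them.
- A reader might infer that new dialysis is misclassified however creatinine is sampled. It is not: the wording in 11.4.5 counts an earlier peak, and the schedule footnote keeps the highest later value. The gap depends on which values are collected.
- A reader might infer that the most severe renal cases disappear from safety reporting. New dialysis would ordinarily meet the SAE definition in 10.1.1. SAEs are collected throughout (10.1), reviewed by the DSMB (1.2) and reported by arm to day 90 (11.4.5). At most the case is absent from the AKI row.
- A reader might infer that dialysis swings often exceed 1.5-fold. Under the assumed schedule few pairs do; the absolute limb carries the problem.

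**Conclusion.** The point holds for participants on maintenance dialysis. They can enrol, and the printed rule can count their dialysis cycle as AKI. For new renal replacement it holds more narrowly, for starts before the day-5 (±1) draw whose earlier peak is not collected. The effect is a diluted contrast and a possibly incomplete AKI row. The primary analysis is not directly affected.

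The illustrative size is at least about 10-20 false events among 606. It rests on an assumed 5-10% on maintenance dialysis, a thrice-weekly schedule with morning draws and at least one third flagged. The protocol supplies none of these figures. The change is worth making because AKI is an event of special interest and the repair is small.

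**What to change.** Add to both 9.2.4.1 and 11.4.5: *Participants on maintenance renal replacement therapy at baseline are not evaluable for AKI and are left out of its denominator. A new start of renal replacement therapy within 14 days of randomisation counts as AKI irrespective of creatinine.* Record baseline renal replacement with the comorbidities already collected, and any new start from the hospital record.

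Report the creatinine-only version next to it, so that comparison with SNAP remains possible. The cost is two sentences, two yes/no eCRF fields filled from routine records, and a slightly smaller AKI denominator. No eligibility or treatment rule changes.

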11.4.6 Deviation(s) from the original statistical plan

If substantial deviations of the analysis as outlined in these chapters are needed for whatever reason, the protocol will be amended. All deviations of the analysis from the protocol or from the detailed analysis plan will be listed and justified in a separate chapter of the final statistical report.

11.5 Handling of missing data and drop-outs

The primary analysis will be performed on the data available (complete cases). In the sample size calculation, we have included expected proportions of missing data for the individual DOOR components. To keep as many participants as possible in the analysis, we will use the components of the DOOR that are not missing in cases where not all components are missing. For the secondary outcomes, we will consider multiple imputation if the proportion of excluded participants is larger than 5% (the imputation strategy will be pre-specified for each outcome in a separate data analysis plan).

12. QUALITY ASSURANCE AND CONTROL

Written standard operating procedures (SOPs) and manuals of operation will be issued to all sites and adherence to guidance is monitored during site visits.

12.1 Data handling and record keeping / archiving

12.1.1 Electronic Case Report Forms (eCRF)

Relevant clinical study data for each enrolled study participant, i.e., observations, tests and assessments specified in the protocol, are recorded in eCRFs via the web-based electronic data capture (EDC) system implemented in REDCap® at the study centres. The participant's name and address will not be recorded. The EDC system includes guidance for study sites on how to perform data entry and will also be used for query handling.

Local investigators and site trial members will be authorized for the eCRF entries of study participants enrolled at the site. Investigators will be trained to use the EDC system during the site initiation visit. The investigators ensure the accuracy, completeness, and timeliness of the data recorded and provide answers to data queries, as specified in the study protocol and in accordance with additional instructions. The identity of the local investigator entering data, and date and time of data entry will be recorded as meta-data in the study database.

12.1.2 Specification of source documents

Source data will include all study documents (e.g. informed consent forms, online AE/SAE forms, patient data in hospital information system). Source data will be available at all sites and may be found in paper or electronic form.

12.1.3 Record keeping / archiving

The sponsor retains all data relating to the clinical trial for at least twenty years after completion or premature termination of the clinical trial. The local investigators retain all documents necessary for the identification and follow-up of the trial participants and all other original data for at least twenty years after completion or discontinuation of the clinical trial. Data will be stored in the REDCap study database located on servers of the University of Basel. Any study relevant paper documents will be archived at each site for a minimum of 20 years.

12.2 Data management

12.2.1 Data Management System

Study data will be captured via the web-based electronic data capture system REDCap®. The system is developed by Vanderbilt University, US and licensed and hosted by the Department of Clinical Research of the University Basel. The REDCap® software installation and periodical updates are validated by the Department of Clinical Research. All data is stored on servers of the University Hospital Basel in Switzerland. Password protection and user-right management safeguard access, ensuring that only authorized personnel can view or modify the data.

Patients will be entered into REDCap® with a unique study ID. Patient data entry in REDCap® is facilitated by manually entering the unique hospital identification number, which is used to locate and input data at predefined time points. Using data-access groups in REDCap® will ensure that each local investigator (or delegated personnel) can only access data from their respective centre. To enhance data security and confidentiality, the unique hospital identification number is designated as an identifier field in REDCap®, preventing its inclusion in exported datasets. In these exports only the unique study ID of each participant will be included. To ensure that patients can still be correctly identified, each centre will maintain a separate key list that also serves as a site screening and enrolment log file. All data collected is entered into study specific case report forms. An audit trail maintains a record of initial entries and any changes made; time and date of entry; and username of person authorizing entry or change.

12.2.2 Data security, access, and back-up

Data is encrypted at rest and protected by advanced threat detection software according to the security policy of the University Hospital Basel. REDCap® is accessible via a standard browser on devices with internet connection. The data transfer between clients and servers is encrypted using Transport Layer Encryption (TLS) cryptography protocol. Password protection and user-right management ensure that only authorized study investigators, monitors, data managers and local authorities (if necessary) will have access to the data during and after the study.

User administration and user training is performed by the Department of Clinical Research (DKF) Basel according to predefined processes. The built-in audit trail will register any unplanned deviations from the study protocol.

Backup of the REDCap® database is performed daily according to established processes.

12.2.3 Analysis and archiving

REDCap database will be locked after all data has been monitored and cleaned, and all raised queries have been resolved. Data will be archived by the Sponsor for a minimum of 20 years.

12.2.4 Electronic and central data validation

The data managers of the DKF Basel will implement validation rules in REDCap®. When data gets saved in a case report form, it will be validated for discrepancies. The data will be reviewed by the responsible investigator as well as an independent monitor. The monitor will raise queries using the query management system implemented in REDCap®. Designated investigators must respond to the query and confirm or correct the corresponding data. Thereafter the monitor can close the query.

12.3 Monitoring

The Department of Clinical Research of the University of Basel will perform the monitoring of this trial. A monitor from the Department of Clinical Research will, in accordance with the Sponsor, contact all sites for initiation of the trial. According to the scope of the monitoring plan, the monitor will visit the trial site during the study or perform remote monitoring visits, regularly if necessary, and after closing. The monitor will verify the adherence to the protocol, completeness, consistence, and accuracy of the data being entered on eCRF and will thus require access to all patient medical records including laboratory test results and surgery, pathology and radiology reports and supporting documents. The investigator (or his/her delegate) should collaborate with the monitor. They must ensure that source data verification forms, source data and documents are made accessible to the study monitor, and they should answer questions by the Study Monitor in detail to ensure that any problems detected during these visits are resolved. Open action items will be listed and explained by the monitor in follow-up letters and are expected to be resolved in reasonable time.

12.4 Audits and Inspections

In accordance with ICH GCP guidelines [2], audits may be performed by the CEC and CA during the course of the study. The audits will include control of adherence to the protocol, standard operating procedures, ICU GSP guidelines and national legislation. Source data verification and checking of the data entered in the eCRF will be used for assessment of complete and reliable documentation. The local investigators ensure that source data and documents are made accessible to auditors and inspectors and answer their questions. All involved parties must keep the participant data strictly confidential.

